6.1.4 Guidelines for continuation of treatment

For guidelines on the continuation of treatment, refer to [Section 6.3](#) Dose modifications.

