6.3 Dose modifications

6.3.1 Dose modification and dose delay

For patients who do not tolerate the protocol-specified dosing schedule, dose adjustments are permitted in order to allow the patient to continue the study treatment. The following guidelines need to be applied. Any plan to deviate from these guidelines in view of patient safety must be discussed with the sponsor unless there is an urgent need for action.

All dose modifications should be based on the worst preceding toxicity as graded by the NCI Clinical Toxicity Criteria (NCI-CTCAE version 4.03). If study treatment is held due to toxicity, scheduled visits and all assessments as described in [Table 7-1](#) should continue as scheduled, except without dosing. Dose modification guidelines are described in [Table 6-4](#).

If an adverse event is clearly associated to one of study drugs, the dose adjustment directed for that study drug will be followed; however, if the causality is not clear, then it may be necessary to adjust both study drugs. Dosing adjustments will be discussed with the sponsor.

If a patient experiences a DLT then treatment with LDE225 plus INC424 must be stopped and the patient may be discontinued from the study. However, following resolution of the DLT to CTCAE grade 1 or to the patient's baseline value, the patient may continue to receive study treatment at a reduced combination dose level, if appropriate, at the discretion of the investigator and after discussion with the Sponsor.

For each patient, a maximum of 2 dose reductions will be allowed, after which the patient will be required to discontinue study treatment. If the same toxicity returns after re-initiation of treatment at the same dose level, the second re-initiation must resume at a lower dose level. The patient must also discontinue study treatment if, after the treatment is resumed at the lower dose level, the same toxicity recurs with the same or worse severity (except for thrombocytopenia, anemia and neutropenia).

Dose level (-1) is the lowest acceptable dosing level for a patient participating in the study. If a patient cannot tolerate dose level (-1), then study treatment must be discontinued and the patient must be withdrawn from the study. However, if patients in Cohort 1 experience thrombocytopenic DLTs then patients in dose level (-1) will receive INC424 5mg BID and LDE225 200 mg QD.

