7.1.3 Discontinuation of Study Treatment

Patients may voluntarily discontinue from study treatment for any reason at any time. If a patient decides to discontinue from the study treatment, the investigator must make every effort (e.g., telephone, e-mail, letter) to determine the primary reason for this decision and record this information in the patient's chart and on the appropriate eCRF pages. Patients may be considered withdrawn if they state an intention to withdraw, fail to return for visits, or become lost to follow-up for any other reason.

The investigator should discontinue study treatment for a given patient if he/she believes that continuation would be detrimental to the patient's well-being.

Study treatment must be discontinued under the following circumstances:

- Emergence of the following adverse events:
 - Grade 3 or 4 hemorrhagic event of any kind
 - Grade 3 renal toxicity for ≥ 7 consecutive days
 - Grade 4 renal toxicity
 - Grade 4 non-hematologic toxicity
 - Second occurrence of QTcF > 500 ms (\geq Grade 3) or > 60 ms change from baseline on at least two separate ECGs
 - Patient requires or undergoes splenic irradiation
 - Patient requires or undergoes splenectomy
- Any of the following laboratory abnormalities:
 - Grade 4 anemia for ≥ 7 consecutive days despite PRBC transfusions
 - Febrile neutropenia (Grade ≥ 3) (ANC $< 1.0 \times 10^9/L$, with a single temperature of ≥ 38.3 °C or a sustained temperature of ≥ 38 °C for more than one hour)
 - Grade 3 or 4 serum creatinine
 - Bilirubin $> 10.0 \times ULN$
 - Grade 3 or 4 asymptomatic or symptomatic CK elevation with renal function impairment in which CK and creatinine levels do not return to baseline after interrupting treatment
- Pregnancy

- The following deviations from the prescribed dose regimen for LDE225 and INC424:
 - Interruption of study treatment for > 21 days, regardless of reason, from the intended day of the next scheduled dose. However, if the patient is obtaining clinical benefit in terms of response, the patient may continue treatment at the same or at a reduced dose following discussion between the investigator and Novartis.
 - If after 2 dose reductions and after the treatment has resumed at the lower dose, the same toxicity recurs with the same or worse severity (except for thrombocytopenia, anemia, and neutropenia)

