 - If a patient cannot tolerate dose level (-1), which is the lowest acceptable dosing level for this study, except for patients in Cohort 1 who experience thrombocytopenic DLTs and can receive INC424 5mg BID and LDE225 200mg QD.
- Disease Progression
- Use of prohibited treatments (refer to Appendix 1) as determined by Novartis
- Use of another myeloproliferative neoplasm directed therapy
- Any other protocol deviation that results in a significant risk to the patient's safety
- Study is terminated by the Sponsor

Patients who discontinue study treatment should NOT be considered withdrawn from the study. They should return for the assessments indicated in [Table 7-1](#) and [Table 7-2](#). If they fail to return for these assessments for unknown reasons, every effort (e.g. telephone, email, letter) should be made to contact them as specified in [Section 7.1.5](#).

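### The mandatory stop list in Protocol 7.1.3 misrestates 6.3.1: the cap of 2 dose reductions is missing, and two separate stop grounds have become one joint condition

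*Protocol*

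**What the plan says.** Protocol 6.3.1 sets a cap: "For each patient, a maximum of 2 dose reductions will be allowed, after which the patient will be required to discontinue study treatment". That sentence exempts no toxicity. The section then describes a sequence for a recurring toxicity: "If the same toxicity returns after re-initiation of treatment at the same dose level, the second re-initiation must resume at a lower dose level". A second stop follows: "The patient must also discontinue study treatment if, after the treatment is resumed at the lower dose level, the same toxicity recurs", qualified as the same or worse severity and excepting thrombocytopenia, anemia and neutropenia. The word *also* makes this a ground in addition to the cap.

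Protocol 7.1.3 lists the circumstances in which study treatment must be discontinued. Only one of its bullets mentions the number of reductions: "If after 2 dose reductions and after the treatment has resumed at the lower dose, the same toxicity recurs with the same or worse severity", with the same three cytopenias excepted. A neighbouring bullet sets a floor: "If a patient cannot tolerate dose level (-1), which is the lowest acceptable dosing level for this study". No other item in the list restates the cap.

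Protocol 6.1.4 sends the reader back to the dose-modification section: "For guidelines on the continuation of treatment, refer to" Section 6.3.

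**The concern.** These are patient-safety stopping rules. A site deciding whether a patient must stop would naturally turn to the section on discontinuation of study treatment. The bullet there turns an *either/or* into a *both*, so someone working from it alone could keep treating a patient whom 6.3.1 requires to stop.

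Patients who complete 2 years may continue in the extension phase until discontinuation reasons are met (Protocol 4.3.1, 6.1.5), so the list matters for as long as anyone is on treatment. Section 12 of the Protocol allows no authorized deviations. A site following 7.1.3 could therefore breach 6.3.1 without knowing it, and whether to record a deviation would be unclear.

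**Working it through.** No sample-size or error-rate figure is involved. The check compares the two sections as logical conditions and then traces dose sequences through the protocol tables.

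**Rules**

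- 6.3.1: stop if (A) a further reduction would be needed after the 2 allowed, or (B) the same non-cytopenic toxicity recurs at the same or worse severity after resumption at the lower dose level.
- 7.1.3: stop if 2 reductions have been made and the same non-cytopenic toxicity recurs at the same or worse severity.

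Rule A takes the milder reading of the cap sentence. Stopping as soon as the second reduction is made would widen the gap.

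| Situation | 6.3.1 | 7.1.3 bullet |
|---|---|---|
| 2 reductions made, third needed for a different toxicity | stop (A) | no trigger |
| 2 reductions made, third needed for a cytopenia | stop (A, as worded) | no trigger (excepted) |
| 1 reduction made, same non-cytopenic toxicity recurs | stop (B, natural reading) | no trigger |
| 2 reductions made, same non-cytopenic toxicity recurs | stop | stop |

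Every case that meets the 7.1.3 bullet also meets 6.3.1, but not the reverse.

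**Example A: the cap.** The start is the Phase II dose, INC424 20 mg BID plus LDE225 400 mg QD (Amendment 2 rationale), after Week 6.

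1. Grade 2 treatment-related hemorrhage (Table 6-4): INC424 20 − 5 = 15 mg BID, LDE225 unchanged. Reduction 1.
2. Grade 2 thrombocytopenia (Table 6-4): INC424 15 to 10 mg BID, LDE225 unchanged. Reduction 2.
3. Symptomatic Grade 2 CK elevation (Table 6-5): LDE225 400 to 200 mg QD. Reduction 3.

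Under 6.3.1, 3 > 2, so the patient must stop. Under 7.1.3 nothing has recurred, so the joint condition is false. The end dose, INC424 10 mg BID plus LDE225 200 mg QD, is dose level −1 itself (Table 6-2). The floor bullet needs intolerance of that level, so it is false too.

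The example also works without a cytopenia. Replace step 2 with creatinine at 2–3 x ULN, attributed to INC424 and resolving in 8 to 21 days. Table 6-4 then takes INC424 from 15 to 10 mg BID, and the hold does not exceed 21 days.

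**Example B: recurrence.** This reads the lower dose level as the single step down described in the preceding sentence of 6.3.1.

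1. Creatinine at 2–3 x ULN resolves within 7 days and both drugs resume at the same dose (Table 6-4). Reductions: 0.
2. It returns, so the second restart must be lower. If the event is attributed to INC424, only INC424 is lowered, because "If an adverse event is clearly associated to one of study drugs, the dose adjustment directed for that study drug will be followed". Reductions: 1.
3. It recurs at the same severity.

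Under 6.3.1, rule B is met and the patient must stop. Under 7.1.3, 1 < 2, so the joint condition is false. The bullet "Grade 3 or 4 serum creatinine" is not met, because Table 6-4 starts Grade 3 above 3.0 x ULN. If each hold is at most 7 days, the 21-day bullet is not met either.

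Four rows of Table 6-4 hold both drugs and then resume both unchanged: Grade 4 neutropenia, Grade 4 thrombocytopenia, creatinine 2–3 x ULN, and bilirubin above 2 to 3 x ULN (the last two only if resolved within 7 days). The first two are excepted from rule B, so 4 − 2 = 2 rows can start Example B.

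**The case against.** The strongest reply is that nothing contradicts anything. The 7.1.3 list does not say *only*, and it nowhere permits continuation. Where 6.3.1 says stop and 7.1.3 is silent, the answer is stop. The list is also visibly not a full copy of Section 6.3. Table 6-4 discontinues INC424 when bilirubin above 3 to 10 x ULN has not resolved within 7 days, and 4.3.1 then requires both drugs to stop, yet 7.1.3 lists only bilirubin above 10 x ULN. Every reduction in the examples comes from Tables 6-4 and 6-5, inside the section that holds both rules. Section 6.1.4 points there, and dosing adjustments are discussed with the sponsor.

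This stands against the stronger readings a reader might infer: that 7.1.3 withdraws the cap, or that the two sections flatly contradict each other. The documents support neither. These points also lower the practical risk. They do not make the bullet correct: it takes the two conditions of 6.3.1 and joins them wrongly, which is different from leaving them out.

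Two further objections stand in part.

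- It is tempting to state as fact that 7.1.3 moves the recurrence stop from one reduction to two. The recurrence sentence of 6.3.1 gives no number. The single-step reading is the natural one, but 7.1.3 could be taken as spelling out a longer sequence. Example B is conditional on that reading; Example A is not.
- The protocol does not define how reductions are counted across two drugs and different toxicities. SAP 3.3.5 counts a decrease in either drug, but that definition serves tabulation and is not a stopping rule. Example A counts each separate event as one reduction. If reducing both drugs for one event counted as two, the joint condition in 7.1.3 could be reached sooner.

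**Conclusion.** The point holds as a misrestatement. Section 7.1.3 omits the stand-alone maximum of 2 reductions and replaces two stop grounds with one joint condition that is narrower than either. Example A shows the missing cap without relying on the reading of the lower dose level. The recurrence half rests on the natural, but not the only, reading of that phrase.

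No affected-patient count is possible, because the documents give no rates for these sequences. The single-agent INC424 figures in Protocol 1.4.2.2.1 (adverse events requiring reduction or interruption in 55.4%, including 32.4% from thrombocytopenia) show that such dose changes are common. They are not rates of a third reduction or of recurrence after a reduction. A reader might also infer an effect on the spleen-response result or on the Stage 2 decision; nothing in the documents supports that. SAP 1.1 states that Stage 2 will not enroll, so the practical scope is patients still on treatment. The correction should be made because it concerns a safety stop and costs little.

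**What to change.** Replace the single 7.1.3 bullet with two that match 6.3.1:

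- (i) a further dose reduction would be needed after the 2 allowed;
- (ii) a toxicity recurs, no milder than before, once treatment has restarted at the lower dose level, with thrombocytopenia, anemia and neutropenia excepted.

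Ask the sponsor to confirm two matters and state the answers in both sections: whether cytopenia-driven reductions count toward the cap, and how reductions of the two drugs are counted, including when both are lowered for one event. These are clinical choices that the reviewer should not prescribe. As worded, the cap in 6.3.1 has no cytopenia exception, but Protocol 6.3.2.1 and Table 6-6 allow INC424 to be raised again after platelet-driven decreases. Amendment 2 lists 7.1.3 as updated and does not list 6.3.1, so the sponsor should also confirm that 6.3.1 is the intended rule.

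The wording change is one bullet into two at the next amendment, plus the sponsor's clarifications. No new data, visits or outputs are needed: dose reductions are already listed under SAP 3.3 and protocol deviations under SAP 3.2.2.

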6.2.5 Definitions of dose limiting toxicities (DLTs)

A dose-limiting toxicity (DLT) is defined as an adverse event or abnormal laboratory value assessed as unrelated to disease progression, inter-current illness, or concomitant medications that meets any of the following criteria in [Table 6-3](#).

For the purpose of dose escalation decisions, only DLTs occurring during the first 6 weeks of study treatment will be necessarily considered and included in the BLRM.

[figure not shown]
Toxicity will be assessed using the NCI Common Terminology Criteria for Adverse Events, version 4.03 (evs.nci.nih.gov/ftp1/CTCAE) unless otherwise specified.

The investigator must notify the Sponsor immediately of any unexpected CTCAE grade ≥ 3 adverse events or laboratory abnormalities. Prior to enrolling patients into a higher dose level, CTCAE grade ≥ 2 adverse events will be reviewed for all patients at the current dose level.

For toxicities which, by definition, require a time-window in order to be defined as DLTs (grade 3 non-hematologic toxicity for ≥ 7 consecutive days), a subsequent visit and/or laboratory assessments must be scheduled accordingly. For example, if a grade 3 non-hematologic toxicity is observed, it must also be observed at least 7 days later, with no intervening lower grades, in order to qualify as a DLT.

Table 6-3 Criteria for defining dose-limiting toxicities

| TOXICITY | DLT CRITERIA |
|---|--|
| Hematologic | |
| Blood and lymphatic system disorders | Neutropenia CTCAE Grade 4* |
| | Febrile neutropenia CTCAE Grade ≥ 3 (ANC $< 1.0 \times 10^9/L$ + Fever ≥ 38.5 degrees C) |
| | Thrombocytopenia CTCAE Grade 4 (Platelets $< 25 \times 10^9/L$)* |
| | Hemorrhagic Event CTCAE Grade ≥ 2 |
| | Anemia CTCAE Grade 4 for ≥ 7 days despite PRBC transfusions |
| Non-Hematologic | |
| Gastrointestinal disorders | Vomiting CTCAE Grade ≥ 3 for > 7 days in duration |
| | Nausea CTCAE Grade 3 despite the use of anti-emetic therapy |
| Hepatic | Total bilirubin CTCAE Grade ≥ 3 , with Direct Bilirubin ≥ 0.5 mg/dL |
| | AST/SGOT or ALT/SGPT CTCAE Grade 3 for ≥ 5 consecutive days |
| | AST/SGOT or ALT/SGPT CTCAE Grade 4 |
| CK elevation | CTCAE Grade ≥ 3 |
| Other | Any CTCAE Grade 3 non-hematologic toxicity for ≥ 7 days Any CTCAE Grade 4 non-hematologic toxicity |
| CTCAE version 4.03 will be used for all grading. | |
| * In two consecutive assessments (the second assessment will be considered valid and final) | |

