If a patient requires a dose delay from either study drug of > 21 days due to an LDE225 or INC424 related toxicity, then the patient must be discontinued from the study; however, if the patient is obtaining clinical benefit in terms of response, the patient may continue treatment at the same or at a reduced dose following discussion between the investigator and Novartis. All patients will be followed for AEs and SAEs for 30 days following the last dose of LDE225 and/or INC424.

Dose modifications for toxicities occurring during the DLT-definition period (6 weeks or 42 days) will not be allowed unless the toxicity qualifies as a DLT. After a toxicity has been characterized as a DLT, a patient can resume therapy with a reduced treatment dose according to the guidelines provided in [Section 6.2.5.1](#).

If the administration of study treatment was interrupted for reasons other than toxicity, then treatment with LDE225 and INC424 may be resumed at the same dose.

Patients who experience muscle toxicity, regardless of whether the toxicity meets the criteria described for a DLT, should be followed according to the dosing modifications for LDE225 as per [Table 6-5](#).

Patients who experience hematologic, renal, or hepatic toxicities should receive follow up evaluations as outlined in [Table 6-7](#).

All interruptions or changes to study drug administration must be recorded on the Dosage and Administration Record eCRF.

[figure not shown]

Table 6-4 Criteria for interruption and re-initiation of INC424 and LDE225 treatment

| | |
|--|---|
| Dose modifications for toxicities occurring during the DLT-definition period (6 weeks or 42 days), and considered as treatment-related, will not be allowed until the toxicity qualifies as a DLT. | |
| Worst toxicity (CTCAE 4.03 Grade) | Dose Modifications for INC424 and LDE225 |
| HEMATOLOGICAL | |
| Neutropenia (ANC) (for 2 consecutive assessments within 48 hrs except febrile neutropenia) | |
| Grade 1 (ANC < LLN - $1.5 \times 10^9/L$) Grade 2 (ANC < $1.5 - 1.0 \times 10^9/L$) Grade 3 (ANC < $1.0 - 0.5 \times 10^9/L$) | INC424: Maintain dose level LDE225: Maintain dose level |
| Grade 4 (ANC < $0.5 \times 10^9/L$) | INC424: Hold dose until resolved to \leq grade 1, then maintain dose level LDE225: Hold dose until resolved to \leq grade 1, then maintain dose level |

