| Febrile neutropenia (Grade \geq 3) (ANC < $1.0 \times 10^9/L$, with a single temperature of ≥ 38.3 °C or a sustained temperature of ≥ 38 °C for more than one hour) | INC424: Discontinue study treatment LDE225: Discontinue study treatment |
| Thrombocytopenia (for 2 consecutive assessments within 48 hrs) | |
| Grade 1 (PLT < LLN - $75 \times 10^9/L$) | INC424: Maintain dose level LDE225: Maintain dose level |
| Grade 2 (PLT < $75 - 50 \times 10^9/L$) | INC424: Reduce to 10 mg BID or continue at same dose level (whichever is lower) LDE225: Maintain dose level |
| Grade 3 (PLT < $50-25 \times 10^9/L$) | INC424: Reduce to 5mg BID LDE225: Maintain dose level |
| Grade 4 (PLT < $25 \times 10^9/L$) | INC424: Hold dose until resolved to \leq grade 1, then maintain dose level LDE225: Hold dose until resolved to \leq grade 1, then maintain dose level |
| Hemorrhagic event of any kind (if related to study treatment) | |
| Grade 1 | INC424: Maintain dose level LDE225: Maintain dose level |
| Grade 2 | INC424: Hold dose until resolved completely, then \downarrow by 5 mg BID LDE225: Hold dose until resolved completely, then maintain dose level |
| Grade 3 or 4 | INC424: Discontinue study treatment LDE225: Discontinue study treatment |
| RENAL | |
| Serum creatinine | |
| < 2 x ULN | INC424: Maintain dose level LDE225: Maintain dose level |
| 2 – 3 x ULN | INC424: Hold dose until resolved to \leq grade 1, then: If resolved in \leq 7 days, then maintain dose level If resolved in > 7 days, then \downarrow by 5 mg BID LDE225: Hold dose until resolved to \leq grade 1, then: If resolved in \leq 7 days, then maintain dose level If resolved in > 7 days, then \downarrow 1 dose level |
| Grade 3 (> $3.0 - 6.0 \times ULN$) | INC424: Discontinue study treatment LDE225: Discontinue study treatment |
| Grade 4 (> $6.0 \times ULN$) | INC424: Discontinue study treatment LDE225: Discontinue study treatment |

| | |
|--|---|
| Dose modifications for toxicities occurring during the DLT-definition period (6 weeks or 42 days), and considered as treatment-related, will not be allowed until the toxicity qualifies as a DLT. | |
| Worst toxicity (CTCAE 4.03 Grade) | Dose Modifications for INC424 and LDE225 |
| HEPATIC | |
| Bilirubin (*for patients with Gilbert Syndrome these dose modifications apply to changes in direct bilirubin only). Bilirubin will be fractionated if elevated | |
| Up to 2.0 x ULN | INC424: Maintain dose level LDE225: Maintain dose level |

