| > 2.0 – 3.0 x ULN with ALT or AST ≤ 3.0 x ULN | INC424: Hold dose until resolved to ≤ grade 1, then: If resolved in ≤ 7 days, then maintain dose level If resolved in > 7 days, then ↓ by 5 mg BID LDE225: Hold dose until resolved to ≤ grade 1, then: If resolved in ≤ 7 days, then maintain dose If resolved in > 7 days, then ↓ 1 dose level |
| > 3.0 - 10.0 x ULN with ALT or AST ≤ 3.0 x ULN | INC424: Hold dose until resolved to ≤ grade 1, then: If resolved in ≤ 7 days, then maintain dose level If resolved in > 7 days, then discontinue treatment LDE225: Hold dose until resolved to ≤ grade 1, then ↓ 1 dose level |
| > 10.0 x ULN | INC424: Discontinue study treatment LDE225: Discontinue study treatment |
| AST or ALT | |
| Grade 1 (> ULN – 3.0 x ULN) | INC424: Maintain dose level LDE225: Maintain dose level |
| Grade 2 (> 3.0 - 5.0 x ULN) without total bilirubin elevation to > 2.0 x ULN | INC424: Maintain dose level LDE225: Maintain dose level |
| Grade 3 (> 5.0 - 20.0 x ULN) without total bilirubin elevation to > 2.0 x ULN | INC424: Hold dose until resolved to ≤ grade 1, then: If resolved in ≤ 7 days, then maintain dose level If resolved in > 7 days, then ↓ by 5 mg BID LDE225: Hold dose until resolved to ≤ grade 1, then ↓ 1 dose level |
| Grade 4 (> 20.0 x ULN) without bilirubin elevation to > 2.0 x ULN | INC424: Hold dose until resolved to ≤ grade 1, then ↓ by 5 mg BID LDE225: Hold dose until resolved to ≤ grade 1 or baseline, then ↓ 1 dose level |
| CARDIAC | |
| Cardiac – QTc prolongation | |
| QTcF > 500 ms (≥ Grade 3) or > 60 ms change from baseline on at least two separate ECGs | Perform an analysis of serum potassium and magnesium, and if below lower limit of normal, correct with supplements to within normal limits. Concomitant medication usage must be reviewed. Perform a repeat ECG within one hour of the first QTcF of > 500 ms. If QTcF remains > 500 ms, repeat ECG as clinically indicated but at least once a day until the QTcF returns to < 480 ms. INC424: Hold dose until QTcF prolongation has resolved, then ↓ by 5 mg BID LDE225: Hold dose. Once QTcF prolongation has resolved, study treatment may be restarted at ↓ 1 dose level Second Occurrence: Discontinue patient from further study treatment with both medications |
| Other non- hematological adverse events | |
| Grade 1 or 2 | INC424: Maintain dose level LDE225: Maintain dose level |

| | |
|---|--|

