| Cardiac | If \geq grade 3 (QTcF $>$ 500 msec as identified by the investigator on the ECG reading or $>$ 60 ms change from baseline on at least 2 separate ECGs taken within 1 hour): The patient must be hospitalized or monitored by the investigators with hourly ECGs until the QTcF is \leq 500 msec and $<$ 30 msec from baseline. Immediate attention to potassium and magnesium and other clinical factors such as oxygenation, ischemia, and the like will be addressed. A plasma sample should be drawn to assess the concentration of LDE225, magnesium and potassium at the time when the absolute QTcF $>$ 500 msec. Once QTcF prolongation has resolved, reinstate treatment according to Table 6-4 and perform ECG monitoring weekly. If the ECGs obtained in the first 6 weeks after dose reduction are without any QTcF $>$ 500 msec and QTcF change from baseline \geq 60 msec, then ECG monitoring should be performed every 4 weeks. |

[figure not shown]

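### The 42-day ban on dose changes does not exempt the QTcF > 500 ms hold, and Section 6.2.5 stops febrile neutropenia one episode later than Table 6-4 and Section 7.1.3

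*Protocol*

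**What the plan says.** **The ban.** Section 6.3.1 says of dose modification for toxicities arising in the DLT-definition period: "6 weeks or 42 days) will not be allowed unless the toxicity qualifies as a DLT". The header running across Table 6-4 puts it slightly differently, for events in the same period "and considered as treatment-related, will not be allowed until the toxicity qualifies as a DLT". Section 6.3.1 contains one exception: muscle toxicity follows Table 6-5 whether or not it is a DLT. The header does not repeat that exception.

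**QTcF.** The cardiac row of Table 6-4 sits under the header. For QTcF above 500 ms, labelled Grade 3 or higher, it holds both drugs. The INC424 instruction is "Hold dose until QTcF prolongation has resolved"; LDE225 is also held, and each drug restarts lower. Table 6-7 does not carry the header, and it continues "Once QTcF prolongation has resolved, reinstate treatment according to" Table 6-4. Table 6-3 has no QTc criterion. The event can be a DLT only through the catch-all row, "Any CTCAE Grade 3 non-hematologic toxicity for" 7 days or longer, or at Grade 4.

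**Stops.** The febrile-neutropenia entry in Table 6-4 is "INC424: Discontinue study treatment LDE225: Discontinue study treatment", with no episode count, and Section 7.1.3 lists the same event as a mandatory stop. Section 6.2.5, in its list of DLTs that end treatment, names febrile neutropenia only at a second episode. For the kidney, the laboratory list in 7.1.3 has "Grade 3 or 4 serum creatinine" with no duration, and Table 6-4 agrees. Section 6.2.5 and the adverse-event list in 7.1.3 instead name Grade 3 renal toxicity lasting a week or more.

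**The concern.** A site reading the ban literally would not make a planned hold for a QTcF above 500 ms in weeks 1 to 6, although the cardiac row prescribes it and the follow-up table takes it as done. Muscle toxicity has an exception and QTcF has none, so the silence can look deliberate. For febrile neutropenia, a site working from the 6.2.5 list could treat a first episode as compatible with resuming treatment, while two other places end treatment. At stake is whether a safety action is a planned instruction or something the investigator must justify as a departure.

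**Working it through.** No sample-size, power or alpha figure is involved. The check is a cross-reading with some side arithmetic.

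**1. Is the QTcF hold caught by the ban?** Table 6-4 lists holds in the column for dose modifications, under the header. A hold is therefore caught unless the event is already a DLT.

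**2. When does a first QTcF > 500 ms become a DLT?** Grade 3 must be seen again at least 7 days later with no lower grade in between (Section 6.2.5). Grade 4 qualifies at once. An event that resolves sooner never qualifies.

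**3. Timing on the scheduled ECGs** (Section 7.2.2.5.7: screening, Week 1 Day 1, then every 4 weeks, taken pre-dose):
- Week 5 Day 1 = 4 × 7 + 1 = day 29. The next, Week 9 Day 1 = 8 × 7 + 1 = day 57, falls after day 42.
- Persisting Grade 3 found on day 29 is a DLT on day 29 + 7 = day 36 at the earliest.
- With the ±1 day visit window the tracing falls on days 28 to 30, so the earliest DLT falls on days 35 to 37. An unscheduled ECG could find the event earlier.

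**4. Would a hold cost evaluability?** Section 10.1.3 requires at least 75% of planned doses of each drug over 42 days, with at most 10 missed LDE225 and 20 missed INC424 doses. After a hold of d days the share taken is (42 − d)/42 for LDE225 and (84 − 2d)/84 for INC424.

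| Hold (days) | LDE225 | INC424 |
|---|---|---|
| 7 | 35/42 = 83.3% | 70/84 = 83.3% |
| 10 | 32/42 = 76.2% | 64/84 = 76.2% |
| 11 | 31/42 = 73.8% | 62/84 = 73.8% |

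On the missed-dose count, a hold of up to 10 days does not by itself remove a patient from the dose-determining set.

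**5. Stopping rules side by side**

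| Place | Febrile neutropenia | Grade 3 renal |
|---|---|---|
| Section 6.2.5 | 2nd episode | at least 7 days |
| Table 6-4 | 1st episode | creatinine, any duration |
| Section 7.1.3, laboratory list | 1st episode | creatinine, any duration |
| Section 7.1.3, adverse-event list | not listed | at least 7 days |

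For febrile neutropenia, 6.2.5 is the outlier. For creatinine, 7.1.3 requires discontinuation when any listed item is met. A Grade 3 value of any duration meets one, so the 7-day bullets add nothing for creatinine.

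**6. Do these DLT rules end at day 42?** Section 6.2.5 limits only what must enter escalation decisions: "only DLTs occurring during the first 6 weeks of study treatment will be necessarily considered and included in the BLRM". Section 6.3.1, however, calls the 42 days the DLT-definition period. Whether the 6.2.5 list binds later is not settled.

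**7. Reach.** At 06 February 2015 (Amendment 2 rationale), 50 had been treated and 14 had discontinued: 50 − 14 = 36, or 36/50 = 72%, still on treatment. This is a dated headcount, not a number of patients facing these events.

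**The case against.** **Patients are protected anyway.** Section 6.3.1 allows departures for patient safety after discussion with the sponsor, or without it when action is urgent. The Table 6-4 footnote allows case-by-case discussion. Section 7.1.3 tells the investigator to stop if continuing would be detrimental. Table 6-7 requires hospitalization or hourly ECGs, and Section 12.1 expects immediate safety action even if it is a deviation. This stands and limits the harm. It still leaves the QTcF hold as a departure rather than the planned response, and Section 12 says that deviations are not authorized in advance.

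**A hold is not a modification.** The title of 6.3.1 names modification and delay separately, so the ban might cover only dose reductions. But Table 6-4 files holds under dose modifications, so the text does not establish that reading.

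**Section 6.2.5 leads to the right place for febrile neutropenia.** It allows resumption after a DLT only after sponsor consultation and under 6.3.1 and Table 6-4, and Table 6-4 says discontinue. This largely stands: a site that follows the reference stops at the first episode. The second-episode bullet still contradicts that result. Nor is the chain clean, since 6.3.1 refers resumption to 6.2.5.1, which refers back to 6.3.1.

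**Little is left to affect.** SAP Section 1.1 says that Stage 2 will not enrol. Single-agent experience suggests that the events are uncommon: no clinically significant treatment-related ECG changes with LDE225, no apparent adverse ECG effect of INC424, and in the INC424 Phase III myelofibrosis studies dose holds or reductions for neutropenia in 1.3% of patients and discontinuation in 0.3%. This stands, and it sets the severity.

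**Conclusion.** The point holds as a low-to-moderate wording correction. Two rules misdirect if followed literally: the ban suspends the planned QTcF hold for a first event that is not yet a DLT, and the 6.2.5 febrile-neutropenia bullet stops one episode later than two other places. The creatinine wording is redundant rather than contradictory.

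Four stronger readings are tempting but not supported:
- **The ban delays the mandatory stops.** Table 6-4 does place some discontinuations under its header. Section 7.1.3 is a separate section that makes them mandatory with no 42-day limit, so delay is a strained reading.
- **The creatinine rules give opposite instructions.** Failing the 7-day bullet does not cancel the any-duration one, and no text tells the site to continue.
- **The fever thresholds conflict.** The DLT needs 38.5 °C; the stop applies at a single 38.3 °C (0.2 °C lower) or a sustained 38 °C (0.5 °C lower). A stop more cautious than the DLT definition is coherent.
- **Patients have no protection in the window.** The safety clauses above show otherwise.

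The conclusion assumes that a hold counts as a dose modification, as Table 6-4's layout indicates, and that QTcF > 500 ms without Grade 4 features is Grade 3. The QTcF part has little forward effect because no new patient enters the window. The febrile-neutropenia part could matter to patients still on treatment if the 6.2.5 list applies beyond day 42. Their current number is not given, and no document reports that any of these events occurred.

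**What to change.** - In 6.3.1 and the Table 6-4 header, state that the QTcF hold, the Table 6-5 muscle-toxicity rules and the 7.1.3 mandatory stops apply during the 42 days.
- Change the febrile-neutropenia bullet in 6.2.5 to the first episode, matching Table 6-4 and 7.1.3.
- State that the any-duration Grade 3 creatinine stop governs, leaving the 7-day bullets for other renal toxicity.
- Leave the DLT fever threshold as it is.

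The cost is amendment wording, with no added visits, patients or analyses. The benefit is correspondingly modest: consistent instructions for patients still on treatment, and clean text for anyone reusing these rules.
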